9.0 EVALUATION OF SAFETY PARAMETERS

All safety analyses will be performed using the Safety Analysis population.

9.1 Adverse Events

Per protocol, an adverse event is defined as “any untoward medical occurrence in a subject or clinical investigation subject administered a pharmaceutical product and which does not necessarily have a causal relationship with this treatment” (examples delineated in the protocol Section 10.1).

Severity is defined from 1(mild) through 5(fatal), as described in protocol Section 10.2.2.

An AE is considered as treatment emergent (TEAE) if it appears on or after the first dose date of RGI-2001, or was already present and worsened after the first dose date, up to 30 days after the last RGI-2001 dose date. Any medical condition that is present at the time that the subject is screened will be considered as baseline and not be reported as an AE (instead as medical history). However, if the subject’s condition deteriorates at any time during the study, it will be recorded as an AE. Almost all AEs collected on the eCRFs will be considered TEAEs, no onset dates will be imputed. If an onset date is missing/invalid, then only included in listing and not included in summary table. If AE onset date is >30 days after the last RGI-2001 dose date, then it will not be considered a TEAE and therefore not included in the summary tables (only included in the listings).

A summary table of TEAEs with a count and percent of subjects in various TEAE categories will be provided (for example: one or more TEAEs, study-medication related TEAEs, serious TEAEs, discontinued due to TEAEs).

Verbatim adverse events will be mapped to preferred term (PT) and system organ class (SOC) using MedDRA V22.0. All TEAEs will be summarized with frequency counts and percentages by

MedDRA SOC and PT. A subject with multiple occurrences of an AE will be counted only once in the AE SOC-PT category in summary tables.

Incidences of TEAEs by SOC and PT will be summarized by counts and percentages and provided for: (1) overall for all TEAEs and (2) various subsets (for example, Serious TEAEs, Related TEAEs, Grade 3 or 4 TEAEs, etc.).

In addition, incidences of TEAEs by PT (not SOC) will be summarized by counts and percentages and provided for: (1) overall for all TEAEs and (2) various subsets. For these PT-specific summary tables, the following hematologic preferred terms will be grouped and summarized under a common term: thrombocytopenia (i.e., thrombocytopenia and platelet count decreased), leukopenia (i.e., leukopenia and white blood cell count decreased), neutropenia (i.e., neutropenia and neutrophil count decreased), anemia (i.e., anemia and red blood cell count decreased), and lymphopenia (i.e., lymphopenia and lymphocyte decreased).

All AEs will be provided in a by-subject listing, as well as individual AE listings for various subsets (e.g., serious, leading to study discontinuation, etc.).

The by-subject listings will include the duration of each event. Duration will be calculated as the stop date of the event minus the start date, unless the event is determined ongoing at exit. Duration will not be calculated for events with invalid start/stop dates, where invalid is defined as a non-calendar date (e.g., 32-dec-2021, 15-hex-2020).

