- q Evaluation of status of hematologic malignancy should be conducted as per institutional guidelines but should include a bone marrow aspirate and biopsy with cytogenetics, molecular diagnostics and chimerism as appropriate based on disease histology at baseline, and at time intervals close to Days 100, 180 and 365.

- r Adverse events (AEs) must be recorded using National Cancer Institute (NCI) Common Terminology Criteria for Adverse Events (CTCAE v. 5.0) where possible. The reporting period for non-serious AEs starts after the first administration of study drug on Day 0. The reporting period for serious AEs starts after the informed consent form (ICF) has been signed. Adverse event monitoring should be continued for at least 30 days following the last dose of study drug. Infections should be recorded throughout the study. See [Section 10](#) for further details.
- s Review of all medications, including over-the-counter (OTC) preparations and herbal products. Concomitant medications used from 2 days prior to the preparatory regimen before Day 0 through the end of the subject's study participation, should be recorded. Maintenance therapy should be documented as a concomitant medication.

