## 10.2 Adverse Event Reporting

The reporting period for non-serious adverse events starts at the commencement of the infusion of RGI-2001 on Day 0 and continues for at least 30 days following the last dose of study drug. Medical conditions that start after the ICF is signed, but before the first dose of study drug should be recorded on the medical history eCRF.

If an AE remains unresolved 30 days following the last dose of study drug, the subject will be followed, at the investigator’s discretion, until resolution of the event. Resolution is defined as return to baseline status or stabilization of the condition with the expectation that it will remain chronic.

Adverse events (including laboratory abnormalities that constitute AEs) should be described using a diagnosis whenever possible, rather than individual underlying signs and symptoms. When a clear diagnosis cannot be identified, each sign or symptom should be recorded as a separate AE.

The Investigator should ask the subject non-leading questions to determine if any AEs have occurred during the study, since the last study visit. Adverse events may also be recorded when they are volunteered by the subject, or through physical examination, laboratory tests, or other clinical assessments.

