#### 10.3.1 Serious Adverse Events Reporting

SAEs that occur at any time between the signing of the ICF until at least 30 days after the subject has stopped study drug must be reported regardless of the casual relationship to the study drug.

SAEs will be reported immediately (within 24 hours of learning of the event) to the Sponsor or its designee by email using the study-specific SAE Report Form and recorded in the eCRF. In addition to the outcome of the SAE, any medication or other therapeutic measures used to treat the event will be recorded on the appropriate eCRF page(s). Investigators should not wait to collect additional information that fully documents the event before notifying Sponsor or its designee of an SAE. Sponsor may be required to report certain SAEs to regulatory authorities within 7 calendar days of being notified about the event; therefore, it is important that Investigators submit additional information requested by Sponsor or its designee as soon as it becomes available.

Reporting of SAEs to the IRB will be done in compliance with the standard operating procedures and policies of the IRB and with applicable regulatory requirements. Adequate documentation must be obtained by Sponsor or its designee showing that the IRB was properly and promptly notified as required.

The SAE form should be emailed to: [[contact]](mailto:[contact])

The Investigator is encouraged to discuss with the medical monitor any AEs for which the issue of seriousness is unclear or questioned. Contact information for the Medical Monitor is as follows:

[REDACTED]

Any SAE observed after the 30-day follow-up period should only be reported to the Sponsor if the Investigator suspects that the SAE has a causal relationship to the study drug. An SAE should be followed until its resolution or until it is judged to be stable. An assessment should be made at each study visit (or more frequently, if necessary) of any changes in severity of the event, the suspected relationship to the study drug, the interventions required to treat the event, and the outcome of the event.

Recurrent episodes, complications, or progression of the initial SAE must be reported, as follow-up to the original episode, within 24 hours of the Investigator receiving the follow-up information.

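### SAP 9.1 leaves adverse events without a usable onset date out of every TEAE summary table; counting them by default, flagged, would fit the SAP's own premise better

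*SAP*

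**What the plan says.** SAP 9.1 defines a TEAE as an event that starts, or worsens, from the first RGI-2001 dose up to 30 days after the last. It then says: "Almost all AEs collected on the eCRFs will be considered TEAEs, no onset dates will be imputed". The next sentence sets the rule for undated events: "If an onset date is missing/invalid, then only included in listing and not included in summary table". Late events are also removed: "If AE onset date is >30 days after the last RGI-2001 dose date, then it will not be considered a TEAE". SAP 4.3 allows no imputation of missing data outside the time-to-event analyses, and no other section returns the undated events to the incidence tables.

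The Protocol sets what reaches the adverse event form:

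- **Non-serious events (Protocol 10.2):** "The reporting period for non-serious adverse events starts at the commencement of the infusion of RGI-2001 on Day 0". For earlier conditions, "Medical conditions that start after the ICF is signed, but before the first dose of study drug should be recorded on the medical history eCRF".
- **Serious events (Protocol 10.3.1):** the window is wider, covering "SAEs that occur at any time between the signing of the ICF until at least 30 days after the subject has stopped study drug".
- **Infections (Protocol Section 3, footnote on adverse events):** "Infections should be recorded throughout the study".

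SAP 1.1 lists the incidence, nature and severity of treatment-emergent events and SAEs as the primary safety endpoint.

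**The concern.** The rule runs against its own premise. If nearly every recorded event is expected to be treatment-emergent, an event with no usable onset date would more naturally be presumed treatment-emergent until something shows otherwise. The SAP presumes the opposite.

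The effect has one direction. Setting a record aside can reduce a displayed incidence or leave it unchanged, but cannot raise it. It reaches every table built from TEAEs, including the serious, related, Grade 3 or 4, Grade 5, dose-limiting and infection tables. In a 50-subject study, uncommon serious terms rest on one to three subjects, so a single missing date can change the displayed picture. The SAP does not ask for the number of excluded records to be shown with the tables, so a reader of the tables alone could not tell that any had been set aside.

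**Working it through.** The documents give no count or rate of missing onset dates, so there is no planned figure to reproduce. The check has three parts.

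**1. What can be inferred about an undated record**

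| Type of record | Could it be pre-dose? | Could it be more than 30 days after the last dose? |
|---|---|---|
| Non-serious event, not an infection | No, by the collection rule (Protocol 10.2) | Possible, since collection runs for at least 30 days |
| Infection | No, if non-serious | Yes, recorded for the whole study |
| SAE | Yes, collected from consent | Yes, if suspected to be related (Protocol 10.3.1) |
| Event rated related | Onset pre-dose is excluded, since no exposure means Not Related (Protocol 10.2.3) | Possible |
| Run-in DLT | No | No, since it must fall within 30 days of the first dose (Protocol 6.1.1) |

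Counting by default is therefore clearly right for a run-in DLT. It is well supported for non-serious events other than infections, and less certain for SAEs and infections. For scale, if the last dose is on Day 35, the window closes at 35 + 30 = Day 65. Follow-up runs to Day 365, so 365 − 65 = 300 days lie beyond it.

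**2. Effect on a displayed incidence**

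Inputs: n = 50 (SAP 2.3), and each subject counted once per category (SAP Table 10.0). A subject is lost from a category only if no record in that category has a usable onset date. Each such subject costs 1/50 = 2.0 percentage points. The subject counts below are illustrations, with Clopper-Pearson 95% intervals.

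| Subjects with the event | Incidence if all are counted | Displayed after one is dropped |
|---|---|---|
| 1 | 1/50 = 2.0% (0.1 to 10.6) | 0/50 = 0% (0 to 7.1) |
| 3 | 3/50 = 6.0% (1.3 to 16.5) | 2/50 = 4.0% (0.5 to 13.7) |
| 5 | 5/50 = 10.0% (3.3 to 21.8) | 4/50 = 8.0% (2.2 to 19.2) |

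The chance of losing at least one of k subjects, each with one record in the category, is 1 − (1 − m)^k. Here m is the share of records without a usable onset date. It is an assumption, so a range is shown.

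| m (assumed) | k = 5 | k = 10 |
|---|---|---|
| 0.5% | 2.5% | 4.9% |
| 1% | 4.9% | 9.6% |
| 2% | 9.6% | 18.3% |
| 5% | 22.6% | 40.1% |

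**3. Partial dates**

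SAP 4.1 calls a date *invalid* when its day or month is missing, and fills in the 1st or January for time-to-event outcomes. SAP 9.1 gives the word a narrower meaning, a date that does not exist in the calendar, but only for computing event duration. The sentence on onset dates does not say which meaning applies. The listing conventions (SAP Table 11.1.2) provide a code for unknown parts of date variables, so incomplete dates are expected. On the SAP 4.1 meaning, an event whose known month and year lie wholly inside the treatment period would be left out. On the SAP 9.1 meaning, it might not be.

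**The case against.** The strongest reply is that post-dose does not mean treatment-emergent. The collection rule settles only the lower end of the window, and only for non-serious events. SAEs are recorded from consent, so an undated one may belong to the conditioning period. Infections and late related SAEs can arise well after the window closes. Counting everything undated would replace possible undercounting with possible overcounting. This stands, and it is a real cost of the change. It does not rescue the present rule, which also leaves out events that must lie inside the window.

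Three further points limit the size:

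- All events remain in by-subject listings, with separate listings for serious, dose-limiting and fatal events and for infections. Deaths have their own table, 14.1.2.
- Edit checks and queries (Protocol 13.4.2) and 24-hour SAE reporting should resolve most dates, above all for serious events.
- The TEAE tables are descriptive. The suspension rules in Protocol 12.4 use regimen-related toxicity, graft failure and non-relapse mortality, not these tables.

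A reader might infer three stronger things. One is that serious or fatal events disappear from the report. They do not: the loss is confined to the TEAE incidence tables. Another is that every undated record is nearly always treatment-emergent. The wider collection windows for SAEs and infections do not support that. The third is that the SAP plainly discards partial dates. It is ambiguous on this, and the supportable point is that the wording needs settling.

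**Conclusion.** The concern holds in a limited form. SAP 9.1 excludes all events with a missing or invalid onset date from the TEAE summaries, without exception and against its own expectation that almost all recorded events qualify. Relative to counting these records, the rule can only lower a primary safety endpoint. The loss is 2 percentage points of 50 for each subject left with no dated record in a category.

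The total effect cannot be derived from the documents. If queries resolve most dates, it is probably small. The probabilities in the working rest on assumed rates of missing dates and on one record per subject per category. The treatment of partial onset dates is an open ambiguity, and the effect would be larger if they fall under the rule. No test or suspension decision is shown to depend on it. The case for changing the sentence is that the repair is cheap and makes the tables transparent, not that a large bias has been shown.

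**What to change.** Replace the sentence on missing or invalid onset dates in SAP 9.1 with:

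> An AE with a missing, invalid or partial onset date is counted as a TEAE unless the known part of the onset date, or the stop date, shows that it began before the first dose without worsening, or more than 30 days after the last dose; such records are flagged in the listing and their number is footnoted in the summary tables.

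This classifies the event without assigning it a date, so the bar on imputing onset dates and SAP 4.3 can stay as they are. Naming partial dates removes the ambiguity between SAP 4.1 and SAP 9.1.

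The cost is one SAP sentence, a flag and a footnote, with no new data. The downside is that a few undated pre-dose SAEs, or undated infections or related SAEs from beyond the 30-day window, could be counted as treatment-emergent. The flag and footnote let a reader see how many records are involved and judge them individually.

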The pharmacologic actions of RGI-2001, manifested by a decrease in iNKT cells, could result in an impaired immune response to various pathogens and in absolute changes in T-cell or B-cell lymphocyte counts. Additionally, the ability of RGI-2001 to induce a tolerogenic state could result in undesirable tolerance to antigens to which subjects are exposed in the interval surrounding the administration of RGI-2001.

Literature reports have linked the activation of iNKT cells with the progression of atherosclerosis in murine models of atherogenesis (Tupin 2004). The role of iNKT cells in the development of atherosclerotic lesions in humans is unknown; however, inflammation and the innate immune response are believed to contribute to the progression of atherosclerosis. Pharmacologically active doses of RGI-2001 are expected to activate iNKT cells and theoretically could, as a result, aggravate underlying atherosclerotic disease. Only subjects with adequate cardiovascular function without ischemia or myocardial infarction in the previous six months will be enrolled in the clinical study.

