## 9.4 Safety Assessments

Safety will be assessed by clinical laboratory studies, time to myeloid and platelet engraftment and by monitoring of AEs.

Potential safety issues associated with the route of administration or the pharmacology of RGI-2001 include hypersensitivity to RGI-2001, organomegaly, microgranuloma, and infections. Subjects will be monitored closely for hypersensitivity reactions to RGI-2001. Infections will be recorded throughout the study. Subjects will be followed for 30 days following end of treatment and monitored for the occurrence of adverse events by means of physical examination, and laboratory testing, including hematology, T-cell, immunophenotyping, other serum chemistry, urinalysis and liver function tests.

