9.2 Infections

Incidence of any TEAE infection will be provided, as well as a frequency distribution to describe the type of infection (e.g., bacterial/viral/fungal). These will also be provided in a by-subject listing.

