Table Number and Title	Analysis Population
Table 14.3.1.4: Related TEAEs – Incidence by SOC and Preferred Term (Safety Population)	Safety Analysis
Table 14.3.1.5: Serious and Related TEAEs – Incidence by SOC and Preferred Term (Safety Population)	Safety Analysis
Table 14.3.1.6: Grade 3 or 4 TEAEs – Incidence by SOC and Preferred Term (Safety Population)	Safety Analysis
Table 14.3.1.7: Grade 3 or 4 TEAEs and Related – Incidence by SOC and Preferred Term (Safety Population)	Safety Analysis
Table 14.3.1.8: Grade 5 TEAEs – Incidence by SOC and Preferred Term (Safety Population)	Safety Analysis
Table 14.3.1.9: Grade 5 TEAEs and Related – Incidence by SOC and Preferred Term (Safety Population)	Safety Analysis
Table 14.3.1.10: TEAEs occurring in $\geq 20\%$ of Subjects– Incidence by SOC and Preferred Term (Safety Population)	Safety Analysis
Table 14.3.1.11: TEAEs – Incidence by SOC and Preferred Term, and Worst Grade (Safety Population)	Safety Analysis
Table 14.3.1.12: Grade 3 or 4 TEAEs – Incidence by SOC, Preferred Term, and Worst Grade (Safety Population)	Safety Analysis
Table 14.3.1.13: Grade 3 or 4 TEAEs and Related – Incidence by SOC, Preferred Term, and Worst Grade (Safety Population)	Safety Analysis
Table 14.3.1.14: TEAEs occurring in $\geq 20\%$ of Subjects– Incidence by SOC, Preferred Term, and Worst Grade (Safety Population)	Safety Analysis
Table 14.3.1.15: TEAEs Leading to RGI-2001 Dose Interruption or Reduction – Incidence by SOC, Preferred Term, and Worst Grade (Safety Population)	Safety Analysis
Table 14.3.1.16: TEAEs Leading to Discontinuation of RGI-2001 – Incidence by SOC, Preferred Term, and Worst Grade (Safety Population)	Safety Analysis
Table 14.3.1.17: TEAEs Leading to Discontinuation from the Study – Incidence by SOC, Preferred Term, and Worst Grade (Safety Population)	Safety Analysis
Table 14.3.1.18: TEAEs with Dose-Limiting Toxicity – Incidence by SOC, Preferred Term, and Worst Grade (Safety Population)	Safety Analysis
Table 14.3.1.19: Infection TEAEs – Incidence by SOC, Preferred Term, and Worst Grade (Safety Population)	Safety Analysis
Table 14.3.1.20: TEAEs – Incidence by Preferred Term (Safety Population)	Safety Analysis
Table 14.3.1.21: Related TEAEs – Incidence by Preferred Term (Safety Population)	Safety Analysis
Table 14.3.1.22: Serious TEAEs – Incidence by Preferred Term (Safety Population)	Safety Analysis
Table 14.3.1.23: Grade 3 or 4 TEAEs – Incidence by Preferred Term (Safety Population)	Safety Analysis

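### Infections are recorded for the whole study but summarised only up to 30 days after the last dose; later infections, and any late related SAEs, reach listings but no AE, SAE or infection summary table

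*SAP*

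**What the plan says.** **Collection (protocol).** Section 9.4 lists infections among the potential safety issues linked to the drug's route or pharmacology, and adds: "Infections will be recorded throughout the study". Footnote r of the Schedule of Assessments (Section 3) repeats the instruction: "Infections should be recorded throughout the study". Section 4.6 gives the reason, naming an "impaired immune response to various pathogens" as a possible pharmacological effect. Other AEs are collected for at least 30 days after the last dose (Section 10.2). For SAEs beyond that point, Section 10.3.1 sets a restricted rule: "Any SAE observed after the 30-day follow-up period should only be reported to the Sponsor if the Investigator suspects" a causal link to the study drug.

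**Tabulation (SAP).** Section 9.1 defines a TEAE as an event that starts or worsens from the first dose up to 30 days after the last. On later onsets it says "If AE onset date is >30 days after the last RGI-2001 dose date, then it will not be considered a TEAE", and that such an event is "therefore not included in the summary tables (only included in the listings"). Section 9.2 then carries the restriction over to infections: "Incidence of any TEAE infection will be provided". Section 11.2 plans "Table 14.3.1.19: Infection TEAEs" and Table 14.3.1.32, which gives treatment-emergent infections by type. All of Tables 14.3.1.1 to 14.3.1.32 are titled as treatment-emergent.

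**The concern.** The protocol extends collection beyond 30 days for two kinds of event: all infections, and SAEs that the investigator suspects are due to RGI-2001. The SAP applies the general AE window to both and plans no supplementary summary.

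Infection is a risk that the protocol itself takes seriously. Section 4.6 says that a fall in lymphocyte subsets may increase susceptibility to some infections. The Grade 4 events it reports from the first-in-human study are sepsis in one subject and septic shock with respiratory failure in another. Both subjects were in the 100 µg/kg group.

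At stake is how the safety results read beside the efficacy results. Chronic GvHD, OS, DFS, NRM and GRFS are all followed to one year, while infection incidence would stop at about Day 65. One-year NRM would include a late infection death, but no infection or Grade 5 table would show the cause. A late related SAE could be reported while the serious-and-related table shows none.

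**Working it through.** The plan gives no figure to reproduce here. The check is a comparison of collection with tabulation, followed by day arithmetic.

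**Step 1: is there any table that is not restricted to TEAEs?** I went through the titles in SAP Table 11.2.

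- Tables 14.3.1.1 to 14.3.1.32 (AEs, SAEs, related events, Grade 5 events, DLTs, infections) are all titled TEAE or Treatment-Emergent.
- Table 14.1.2 (Deaths) and Table 14.2.2.6 (NRM) are not restricted, so late deaths are counted there. Neither title indicates a split by infection type or by relatedness.
- Listings 16.2.7.1 (AEs), 16.2.7.2 (SAEs), 16.2.7.6 (AEs leading to death) and 16.2.7.8 (infections) would show late events subject by subject.

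**Step 2: how much recording time falls outside the tables?**

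Inputs:
- planned last dose on Day 35, visit window ±1 day (Protocol 6.1, 8.6 and Section 3);
- cut-off 30 days after the last dose (SAP 9.1);
- follow-up to Day 365 (Protocol Section 3 and 6.7).

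Formulas: last tabulated onset day = day of last dose + 30. Untabulated days = 365 − last tabulated onset day.

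| Last dose | Last tabulated onset | Untabulated days | Share of 365 |
|---|---|---|---|
| Day 35 (planned) | 35 + 30 = Day 65 | 365 − 65 = 300 | 82.2% |
| Day 36 (upper visit window) | 36 + 30 = Day 66 | 365 − 66 = 299 | 81.9% |
| Day 49 (assumes a two-week delay of the last dose) | 49 + 30 = Day 79 | 365 − 79 = 286 | 78.4% |
| Day 0 only (stops after one dose) | 0 + 30 = Day 30 | 365 − 30 = 335 | 91.8% |

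These are shares of calendar time for a subject followed to Day 365. They are not shares of events.

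**Step 3: late SAEs.** Apart from infections, the only SAEs that the protocol asks for after the 30-day period are those suspected to be related. Any that occur are therefore the kind that the related tables exist to show, yet by onset date they fall outside those tables.

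**The case against.** The 30-day window is an ordinary convention and fits the protocol. The primary safety endpoint is worded in terms of treatment-emergent AEs, Section 9.4 describes 30 days of AE monitoring after treatment, and nothing in the protocol promises a one-year infection summary. SAP 9.1 also expects that nearly all AEs on the eCRFs will be treatment-emergent. With 50 treated subjects, a late related SAE is an individual case that can be read from a listing.

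Most of this stands. The TEAE definition is not at fault, the SAP does not contradict the planned endpoint, and the argument for a table is weaker for late SAEs than for infections. It does not answer the infection point. A listing gives no incidence, and a general expectation about AEs cannot be relied on for the one category that is recorded to study end.

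A reader might infer more than the documents support:

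- **That late events vanish from the report.** They do not. They are listed, and late deaths are tabulated.
- **That 82% of infections go uncounted.** The figure is days. No late-event rates are given, and infections need not be spread evenly over the year.
- **That late related events belong in the existing related tables.** Those tables are titled TEAE, so adding late events would break the SAP's own definition. It would also mix two collection rules, since after the window only suspected-related SAEs are required.
- **That SAP 9.1 understates on-treatment incidence by leaving AEs with a missing onset date out of the tables.** Because infections are recorded all year, an undated infection could lie well outside the window. The documents do not settle the direction.

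**Conclusion.** The gap is real and limited. The protocol follows infections to the end of the study as a named potential safety issue, and the SAP summarises them only to about Day 65 for a fully dosed subject. That leaves 300 of 365 calendar days without an infection table, or between 286 and 335 days across the dosing patterns considered. Any late related SAE is likewise absent from every AE and SAE summary table. A late death is counted, but without infection type or relatedness.

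This rests on the SAP text being followed as written and on follow-up to Day 365; a subject who dies or withdraws earlier contributes fewer days. The number of infections or SAEs affected cannot be derived from the documents. What is missing is a supplementary summary. The primary safety analysis as defined is not wrong.

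**What to change.** Leave the 30-day TEAE definition and Tables 14.3.1.1 to 14.3.1.32 unchanged.

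1. In SAP 9.2 and Table 11.2, add a supplementary table of all recorded infections from first dose to end of study, by type and worst grade, split at 30 days after each subject's last dose.
2. Secondarily, add a separate short table of SAEs and Grade 5 events judged related to RGI-2001 with onset after the window. Footnote it to say that only suspected-related SAEs are required in that period, so that it is not read as a full count of late SAEs.

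The cost is SAP wording and one or two extra table runs, with no protocol change or added patient burden. Infection data are already being recorded. For late SAEs, confirm first that they are entered in the clinical database, because Protocol 10.3.1 asks for them to be reported to the sponsor without restating eCRF entry. The downside is that reported incidence will look slightly less favourable.
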